9.2.3 Medical History

Medical history will be coded by using the Medical Dictionary for Regulatory Activities (MedDRA). For the FAS, medical history will be summarized descriptively by System Organ Class (SOC) and Preferred Term (PT). The corresponding data listing will also be provided.

9.2.4 Prior and Concomitant Medications

Medications will be coded using the World Health Organization Drug Dictionary (WHO-DD) and categorized as follows:

Prior medication: any medication that was administered during the 56 days before the first dose of study drug.

Concomitant medication: medication continued or newly received during the TE period.

Post-treatment medication: medication continued or newly received after the TE period.

A given medication may be classified as a prior medication, a concomitant medication, or a post-treatment medication; both prior and concomitant; both concomitant and post treatment; or prior, concomitant, and post treatment.

If a medication has a missing or partially missing start/end date or time and if it cannot be determined whether it was taken before the first dose of study drug, concomitantly during the TE Period, or after the TE Period, it will be classified as prior, concomitant, and post treatment medication. Details for imputing missing or partial start and/or stop dates of medication are described in [Appendix B](#).

For FAS, prior medications and concomitant medications will be summarized descriptively using frequency tables by: 1) treatment group and overall, preferred name (PN); and 2) treatment group and overall, anatomic class (ATC) level 1, ATC level 2, and PN. Post-treatment medications will be also included in the medication listing.

9.2.5 Study Drug Exposure

Study drug exposure will be summarized based on the Safety Set and will be presented by treatment group.

Duration of study drug exposure (in weeks) will be calculated as: (last dose date of study drug – first dose date of study drug + 1)/7, regardless of study drug interruption.

Study drug exposure (in weeks) will be summarized descriptively by the number of subjects (n), mean, SD, median, min, and max. It will also be summarized by interval, using counts and percentages.

9.2.6 Study Drug Compliance

Study drug compliance will be summarized based on the FAS and will be presented by treatment group and overall.

Study drug compliance will be calculated as: $100 \times [1 - (\text{total number of days of study drug interruption}) / (\text{duration of study drug exposure in days})]$. A study drug interruption on a given day is defined as an interruption of any study drugs on that day. A study drug interruption that

continues through the end of the study participation (i.e., subject does not resume study drug before the end of the study participation) will not be included in the compliance calculation.

Study drug compliance will be summarized descriptively by the number of subjects (n), mean, SD, median, min, and max. It will also be summarized in categories: <80% and ≥80% using frequency tables.

9.2.7 Important Protocol Deviations

An important protocol deviation (IPD) is a deviation that may significantly affect the completeness, accuracy, or reliability of the study data or that may significantly affect a subject's rights, safety, or well-being. IPD rules will be developed and finalized before database lock.

The protocol deviations that should be considered as potential IPDs include, but are not limited to:

- Subject was enrolled in the study despite the violation of inclusion/exclusion criteria
- Subject was less than 80% compliant with study drug for non-safety reasons
- Subject received prohibited concomitant medications
- Subject received the wrong treatment or incorrect doses

Occurrence of any of these events should be considered as potential IPDs, but a blinded team should categorize them as IPDs only if they have the potential to significantly affect the completeness, accuracy, or reliability of the study data or that may significantly affect a subject's rights, safety, or well-being.

IPDs (from the clinical database or from the site deviation log) will be summarized descriptively based on the FAS and presented by treatment group and overall. Additionally, IPDs will be provided in an individual subject data listing.

9.3 Efficacy Analysis

Unless otherwise defined, all efficacy analyses described in this section will be based on the FAS.

9.3.1 Analysis of Primary Efficacy Endpoint

9.3.1.1 Definition of Variable

The primary efficacy endpoint is the absolute change in LCI_{2.5} from baseline through Week 24.

Lung clearance index (LCI): the LCI assessments are derived from N₂-multiple-breath washout (MBW) testing. Each MBW will be performed in multiple replicates for each visit and the final LCI value will be calculated from the technically acceptable washout replicates as graded and determined by a central reader. The following algorithm is used to derive the valid LCI value at each visit based on the multiple attempt replicates:

- When there is only one acceptable replicate at the visit, the LCI values will not be calculated. The assessment for that subject at the corresponding visit will be missing.
- When there are 2 or more acceptable replicates at the visit, the mean of the values for the acceptable replicates will be calculated as the LCI value at the corresponding visit.

9.3.1.2 Primary Analysis

The primary analysis will be performed using a mixed-effects model for repeated measures (MMRM) with the absolute change from baseline at each post-baseline visit as the dependent variable. The model will include treatment group, visit, and treatment-by-visit interaction as fixed effects, with continuous baseline LCI_{2.5} and weight at Screening (<30 versus ≥30 kg) as covariates. The model will be estimated using restricted maximum likelihood. Denominator degrees of freedom for the *F*-test for fixed effects will be estimated using the Kenward-Roger approximation². An unstructured covariance structure will be used to model the within-subject errors. If the model estimation does not converge, a compound symmetry covariance structure will be used instead. Conditional on the observed data and covariates, missing data will be assumed to be missing at random and therefore will be handled by MMRM model.

The primary result obtained from the model will be the estimated treatment difference through Week 24 (defined as the average of Weeks 4, 8, 16, 24). Data obtained from Day 15, Week 4, Week 8, Week 16, and Week 24 Visits will be included in the model, but the Day 15 Visit will not be included in the estimation of the average treatment effect through Week 24. The least squares (LS) mean estimate with a 2-sided 95% CI and a 2-sided *P* value will be provided. The treatment difference at each post-baseline visit, obtained from the model, will also be provided.

The LS mean (with SE) obtained from the MMRM analysis at each post-baseline visit up to Week 24 will be plotted by treatment group. In addition, the post-baseline raw values and the absolute change from baseline at each post-baseline visit up to Week 24 will be summarized descriptively (n, mean, SD, median, minimum, and maximum).

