8.1 Inclusion Criteria

1. Subject's legally appointed and authorized representative (e.g., parent or legal guardian) will sign and date informed consent form (ICF) and subject will sign an assent form (if applicable).
2. Willing and able to comply with scheduled visits, treatment plan, study restrictions, laboratory tests, contraceptive guidelines, and other study procedures.
3. Subjects (male and female) 6 through 11 years of age, inclusive, on the date of informed consent.
4. Subjects who weigh ≥ 15 kg without shoes at the Screening Visit.
5. Confirmed diagnosis of CF as determined by the investigator.
6. Subjects heterozygous for *F508del* and an MF mutation that is not responsive to IVA and TEZ/IVA (F/MF genotypes, Appendix A).
 - Genotype should be confirmed at the Screening Visit.
 - If the screening CFTR genotype result is not received before the first dose of study drug, a previous CFTR genotype laboratory report may be used to establish eligibility.
 - Subjects who have been enrolled and whose screening genotype does not confirm study eligibility must be discontinued from the study (Section 9.9).
7. Subjects with forced expiratory volume in 1 second (FEV₁) value $\geq 70\%$ of predicted normal for age, sex, and height using equations of the Global Lung Function Initiative (GLI)¹² as determined by spirometry at screening (Section 11.3.2).
8. Subjects with a screening LCI_{2.5} result ≥ 7.5 (Section 11.3.1).
9. Subjects with stable CF disease at the start of the Treatment Period as deemed by the investigator.
10. Subjects who are willing to remain on a stable CF medication regimen (other than *CFTR* modulators) through Week 24 or, if applicable, through the Safety Follow-up Visit
11. Subjects who are able to swallow tablets.
12. As judged by the investigator, the parent or legal guardian must be able to understand protocol requirements, restrictions, and instructions and the parent or legal guardian should be able to ensure that the subject will comply with and is likely to complete the study as planned.

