9.2 Method of Assigning Subjects to Treatment Groups

Subjects will be randomized (1:1) to the ELX/TEZ/IVA or placebo group. Randomization will be stratified by LCI_{2.5} determined at the Screening Visit (<10 versus ≥10) and weight at the Screening Visit (<30 kg versus ≥30 kg).

An interactive web response system (IWRS) will be used to assign subjects to treatment. The randomization code will be produced by Vertex Biostatistics or a qualified randomization vendor. The Vertex study biostatistician will review and approve the production of the final randomization list, which will be reviewed and approved by a designated unblinded biostatistician who is not a member of the study execution team (SET).

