12.1 Sample Size and Power

Approximately 108 subjects will be enrolled and randomized (1:1) to the ELX/TEZ/IVA group or the placebo group.

Power for Primary Efficacy Endpoint

The primary efficacy endpoint is the absolute change in $LCI_{2.5}$ from baseline through Week 24. The primary null hypothesis to be tested is that the mean absolute change in $LCI_{2.5}$ from baseline through Week 24 is the same for the 2 treatment groups, ELX/TEZ/IVA and placebo. The null hypothesis will be tested at a 2-sided significance level of 0.05.

Assuming a within-group SD of 1.5 and a treatment difference of -1.0 between ELX/TEZ/IVA and placebo, a sample size of 49 subjects completing the Treatment Period in each group for a total of 98 subjects will have approximately 90% power for the $LCI_{2.5}$ hypothesis testing, based on a 2-sided 2-sample t-test at a significance level of 0.05. Assuming a 10% dropout rate, approximately 108 subjects will be enrolled.

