9 STATISTICAL ANALYSIS

9.1 General Considerations

Continuous variables will be summarized using the following descriptive summary statistics: the number of subjects (n), mean, SD, median, minimum value (min), and maximum value (max).

Categorical variables will be summarized using counts and percentages.

Baseline value, unless otherwise specified, will be defined as the most recent non-missing measurement (scheduled or unscheduled) collected before the first dose of study drug in the Treatment Period.

Absolute change from baseline will be calculated as post-baseline value – baseline value.

Relative change from baseline will be calculated as (post-baseline value – baseline value)/baseline value.

Treatment-emergent (TE) Period will include the time from the first dose date of study drug to 28 days after the last dose of the study drug or to the date of completion of study participation, whichever occurs first.

Unscheduled visits: Unscheduled visit measurements will be included in analysis as follows:

- 1) In scheduled visit windows per specified visit windowing rules
- 2) In the derivation of baseline and last on-treatment measurements
- 3) In the derivation of maximum and minimum values during TE period, and maximum and minimum change from baseline values during TE period for safety analyses
- 4) In individual subject data listings as appropriate

Visit windowing rules: The analysis visit windows for protocol-defined visits are provided in [Appendix A](#).

Incomplete/missing data will not be imputed, unless specified otherwise.

Outliers: No formal statistical analyses will be performed to detect or remedy the presence of statistical outliers, unless specified otherwise.

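### The primary MMRM has no term for the randomization factor screening LCI2.5; its model SE can be from about right to about 4% too wide, and adding screening LCI2.5 is a low-cost improvement

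*SAP*

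**What the plan says.** Protocol 9.2 sets two stratification factors: "Randomization will be stratified by LCI_{2.5} determined at the Screening Visit (<10 versus ≥10) and weight at the Screening Visit", the latter cut at 30 kg. SAP 7.3 repeats them.

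For the primary analysis, SAP 9.3.1.2 fits treatment, visit and their interaction, and adjusts "with continuous baseline LCI_{2.5} and weight at Screening"; weight is used in the two categories that served for randomization. No screening LCI2.5 term appears. Protocol 12.3.3.1 leaves the choice of covariates to the SAP, so the two documents do not conflict.

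SAP 9.1 defines baseline as the "most recent non-missing measurement (scheduled or unscheduled) collected before the first dose of study drug". The schedule of assessments places one washout test at Screening and another on Day 1. Baseline is therefore normally the Day 1 value, and the Screening value only if Day 1 gives no valid result. Protocol 11.3.1 allows the Screening test before or after bronchodilator; later tests should be pre-bronchodilator.

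**The concern.** Stratified randomization balances the arms on the stratification factor, which lowers the true variance of the treatment difference. A model without that factor leaves its contribution in the residual variance. The reported SE then exceeds the true SE, the interval is too wide, and the test runs below its nominal level.

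Here the factor is partly covered by continuous baseline LCI2.5, so the question is what remains. The stratum is not a function of the model covariate, because it comes from another test on another day. The outcome is a change from Day 1, so measurement error in the Day 1 test enters it directly. A second pre-randomization reading helps to separate that error from the child's true level. At stake is some precision in the primary result. Validity is not at stake.

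**Working it through.** **1. The plan's own figure.** From Protocol 12.1 and SAP 7.2: SD 1.5, difference −1.0, 49 completers per group, two-sided 0.05.
- Planning SE = 1.5 × √(2/49) = 0.303.
- Power = 90.4% (noncentral t) or 91.0% (normal approximation). The stated 90% reproduces.
- Dropout: 98/0.9 = 109, against about 108 stated.
- This is an unadjusted t-test and takes no credit for covariates.

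**2. Assumptions.** The documents give neither the distribution nor the repeatability of LCI2.5. Let τ be the between-child SD of the true level and σ the visit-to-visit error SD. SD 1.5 is applied to the averaged change (Weeks 4, 8, 16, 24), because the Synopsis ties it to the primary endpoint. With complete data, ANCOVA on the four-visit average stands in for the MMRM.

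**3. What a second reading is worth (large-sample, true change unrelated to level, no truncation at 7.5).**
- Residual variance given baseline: R₁ = 2.25 − σ⁴/(τ²+σ²).
- Further reduction from continuous screening LCI2.5: Δ = τ⁴σ² / [(τ²+σ²)(2τ²+σ²)].
- SE = √(R × 2/49).

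| τ | σ | R₁ | Δ | SE, baseline only | SE, plus continuous screening | Change |
|---|---|---|---|---|---|---|
| 1.5 | 0.3 | 2.247 | 0.042 | 0.303 | 0.300 | −0.9% |
| 1.5 | 1.0 | 1.942 | 0.283 | 0.282 | 0.260 | −7.6% |
| 1.5 | 1.2 | 1.688 | 0.333 | 0.262 | 0.235 | −10.4% |

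Simulation, which includes truncation and the lost degree of freedom, gives about −0.4% to −10%.

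**4. What the binary stratum is worth (large-sample).** Grid: mean LCI2.5 9 to 11, τ 1.0 to 2.0, σ 0.3 to 1.0, slope of true change on true level 0 or −0.2, and the entry limit "Subjects with a screening LCI_{2.5} result ≥ 7.5" applied. Adding the stratum multiplies the SE by 0.964 to 0.9996.
- For σ of 0.3 to 0.6, the SE falls by 0.04% to 1.2%, and power rises by at most about 0.6 points.
- At the extreme (mean 9, τ 2.0, σ 1.0), it falls from 0.284 to 0.273, and power goes from 94.1% to 95.5%.
- With the stratum in place of continuous baseline, the SE is 0.1% to 22% larger.

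**5. Model SE against true SE.** Simulation of 98 completers, blocks of 4 within the four strata, mean LCI2.5 10, 4,000 replicates:

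| Scenario | Model | Model SE | True SE | Type I error |
|---|---|---|---|---|
| σ 1.0 | as planned | 0.279 | 0.275 | – |
| σ 1.0 | plus stratum | 0.270 | 0.273 | – |
| σ 1.0 | plus continuous screening | 0.261 | – | – |
| σ 1.2, τ 1.2 | as planned | 0.247 | 0.238 | 0.041 |
| σ 1.2, τ 1.2 | plus stratum | 0.237 | 0.237 | 0.050 |

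- Excess width as planned: 0.279/0.275 = 1.015 and 0.247/0.238 = 1.038.
- Cross-check on size: 2 × P(Z > 1.96 × 1.038) = 0.042, in line with 0.041.
- Simulation error: 1.96 × √(0.05 × 0.95/4000) = ±0.007 on type I error; about 1/√8000 = 1.1% (one standard error) on a true SE.
- At σ 0.5 the planned model SE is 0.301, the stratum brings essentially nothing, and continuous screening LCI2.5 gives 0.296.
- A further run with σ 0.3 to 0.7 gave type I error of 0.045 to 0.052 for the planned model, within simulation error of 0.05. The stratum changed the model SE by +0.2% to −1.5%.
- Over σ 0.3 to 1.2, the stratum changes the model SE by +0.2% to −5%. Type I error as planned nears 0.04 only at σ of 1.0 or more.

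**The case against.** The strongest reply is that LCI2.5 is not ignored. The model adjusts for the same measure in its more efficient continuous form, so the missing cut-point is a detail. Much of this stands. Baseline LCI2.5 must stay, and if LCI2.5 is highly repeatable almost nothing is left for the stratum to add. Each visit value is already the mean of at least two acceptable replicates (SAP 9.3.1.1), which argues against assuming very large error. At low error the binary term even raises the SE slightly. The reply does not show that the stratum is redundant, because Screening and Day 1 are different measurements.

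A reader might infer a larger effect: variance cuts of up to 14% from the stratum and 34% from continuous screening LCI2.5. Those figures need SD 1.5 to be the SD of a single-visit change, with all of that change being noise, so that σ = 1.5/√2 = 1.06 and no child differs in course or response. The Synopsis does not support that reading, since it attaches the SD to the through-Week-24 endpoint.

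A reader might also extend the point to sweat chloride, because SAP 9.3.2.2 uses the same model. Nothing in the documents shows that screening LCI2.5 predicts change in sweat chloride, and no calculation was made for it.

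**Conclusion.** The point holds in a limited, conditional form. The primary model omits a randomization factor that its baseline covariate captures mostly but not wholly. Under the assumed error SD of 0.3 to 1.2, with SD 1.5 for the averaged change, the model SE is between about correct and about 4% too wide.

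Protocol 12.1 says: "The null hypothesis will be tested at a 2-sided significance level of 0.05". The actual level would be about 0.04 to 0.05. It would be tempting to conclude that the SE is too wide whatever the data, or that the power is compromised. Neither follows. The excess vanishes when repeatability is good, any error is on the conservative side, and the sample size took no credit for covariates.

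The size rests on assumed LCI2.5 repeatability and on an ANCOVA approximation with complete data. The sponsor could narrow the range with its own repeatability figures. The change is worth making because it costs so little, but the planned analysis is valid without it.

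**What to change.** In SAP 9.3.1.2, add screening LCI2.5 to the covariates, keeping continuous baseline LCI2.5 and the screening weight category. Continuous screening LCI2.5 is preferred; the <10/≥10 stratum is acceptable. Name the value to be used, since Protocol 9.1.1.1 allows one repeat of a screening test; the natural choice is the value on which the child was stratified.

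Because SAP 9.3.2.2 takes over the primary model, state there whether the added term applies to sweat chloride, and list that model's covariates.

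The cost is one phrase and one degree of freedom. The value exists for every eligible child, since entry depends on it, so no child is lost. No protocol change is needed, and SAP section 4 allows amendment before database lock and unblinding.

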9.3.2 Analysis of Secondary Endpoint

9.3.2.1 Definition of Variable

Sweat chloride (SwCl): the SwCl value for a given visit will be calculated as the mean of the non-missing sweat chloride measurements obtained on the left and right arms at that visit. If one of the two arm measurements at a time point is missing, the other will be used as the mean. A volume ≥15 µL is required for an accurate determination of sweat chloride. Any results reported as having volume <15 µL will be considered missing. Any sweat chloride values reported as <10 mmol/L or >160 mmol/L will be considered missing.

9.3.2.2 Analysis Method

Absolute change in SwCl from baseline through Week 24 will be analyzed based on an MMRM that is the same as the primary efficacy endpoint. Data obtained from Day 15, Week 4, Week 8, Week 16, and Week 24 Visits will be included in the model, but the Day 15 Visit will not be included in the estimation of the average treatment effect through Week 24. The primary result obtained from the model will be the estimated treatment difference through Week 24 (defined as the average of Weeks 4, 8, 16, 24). The LS mean estimate with a 2-sided 95% CI and a 2-sided nominal *P* value will be provided. The treatment difference at each post-baseline visit, obtained from the model, will also be provided.

The LS mean (with SE) obtained from the MMRM analysis at each post-baseline visit up to Week 24 will be plotted by treatment group. In addition, the post-baseline raw values and the absolute change from baseline at each post-baseline visit up to Week 24 will be summarized descriptively (n, mean, SD, median, minimum, and maximum).

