9.3.3 Study Drug Dose and Duration

Study Drug Dose

The dose of ELX/TEZ/IVA evaluated in the pivotal Phase 3 study in subjects with F/MF genotypes ≥12 years of age (200 mg qd/100 mg qd/150 mg q12h) was generally safe and well tolerated and resulted in clinically meaningful improvements compared to placebo in endpoints including ppFEV₁ (LS mean treatment difference of 14.3 percentage points [p<0.0001] for

absolute change from baseline) and SwCl (LS mean treatment difference of -41.8 mmol/L [$p < 0.0001$] for absolute change from baseline) through 24 weeks.

The doses of ELX/TEZ/IVA administered in this study (200 mg qd/100 mg qd/150 mg q12h for subjects ≥ 30 kg, 100 mg qd/50 mg qd/75 mg q12h for subjects < 30 kg) have been selected through assessment of PK over approximately 2 weeks in Part A of a registrational Phase 3 study in 6 to 11 year of age CF subjects, and are the same doses being administered over 24 weeks in Part B of that registrational study.

Treatment Duration

This study will have a 24-week treatment duration to allow for placebo-controlled assessment of safety and efficacy over 24 weeks of treatment.

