12.3.3.1 Analysis of Primary Endpoint

The primary efficacy endpoint is the **absolute change in LCI_{2.5} from baseline through Week 24**. The analysis of this endpoint will be performed using a mixed-effects model for repeated measures (MMRM) with absolute change from baseline in LCI_{2.5} at each post-baseline visit as the dependent variable. The model will include treatment group, visit, and treatment-by-visit interaction as fixed effects, and will be adjusted for main covariates as appropriate. Details will be described in the SAP. The primary result obtained from the model will be the estimated treatment difference through Week 24 (defined as the average of Weeks 4, 8, 16, 24), with a 2-sided 95% CI and a 2-sided *P* value provided. The treatment difference at each post-baseline visit, obtained from the model, will also be provided.

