12.3.3.2 Analysis of Secondary Endpoints

- **Absolute change in SwCl from baseline through Week 24**

The analysis of this pharmacodynamic endpoint will be based on an MMRM model similar to the analysis of the primary endpoint above, with absolute change from baseline in SwCl at each post-baseline visit as the dependent variable.

The primary result obtained from the model will be the estimated treatment difference through Week 24. The LS mean estimate with a 2-sided 95% CI and a 2-sided *P* value will be provided. The treatment difference at each post-baseline visit, obtained from the model, will also be provided.

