	If the last dose date is missing or partial date is reported, the last dose date will be imputed based on, in descending order priority, the Early Treatment Termination (ETT) visit date, last visit date before the Safety Follow-up, or the last study drug administration date from EX SDTM domain, as appropriate. The imputation algorithm will ensure the imputed last dose date does not exceed the study participation end date.		
4.	Sweat Chloride:		
	Non-missing sweat chloride concentrations from the left arm and right arm with assessment end date/time for a given arm up to 30 minutes after first dose time in treatment period will be considered for baseline.		
5.	Electrocardiogram:		
	Baseline is defined as the most recent pretreatment measurement before the first dose of study drug in the Treatment Period. If multiple ECG measurements are obtained on the same calendar day during the TE period,		
	
 ○ For summary purpose, the calculated average ECG will be used as the ECG value on that day; ○ For threshold analysis purpose, all reported ECG values will be used. 		

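### Taken literally, the SAP's sweat chloride MMRM adjusts for baseline LCI2.5 but not for baseline sweat chloride; naming the latter is a nearly free gain in precision.

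*SAP*

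**What the plan says.** SAP 9.3.2.2 (Analysis Method) states that the change in SwCl through Week 24 "will be analyzed based on an MMRM that is the same as the primary efficacy endpoint". It then restates the visits entering the model, the averaging over Weeks 4, 8, 16 and 24, and the nominal status of the P value. It does not restate or change the covariates.

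The primary model in SAP 9.3.1.2 is fitted "with the absolute change from baseline at each post-baseline visit as the dependent variable", with treatment, visit and their interaction, and "with continuous baseline LCI_{2.5} and weight at Screening (<30 versus ≥30 kg) as covariates".

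The protocol is less specific. Section 12.3.3.1 says the primary model "will be adjusted for main covariates as appropriate" and refers to the SAP for details. Section 12.3.3.2 says: "The analysis of this pharmacodynamic endpoint will be based on an MMRM model similar to the analysis of the primary endpoint above".

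Baseline SwCl is available. SAP 9.1 defines baseline in general, SAP 9.2.2 lists SwCl among the continuous baseline disease characteristics, and item 4 of the derived variables in SAP Appendix A sets a timing rule for which readings count as baseline ("Non-missing sweat chloride concentrations from the left arm and right arm with assessment end date/time"). None of these places makes it a model covariate.

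**The concern.** In a change-from-baseline analysis, the endpoint's own baseline is usually the covariate that explains most variance, and it also corrects for chance imbalance between arms. A programmer who follows SAP 9.3.2.2 as written would fit baseline LCI2.5 and the weight stratum and leave baseline SwCl out. Another, reading the instruction as own baseline in each model, would fit something different. SwCl is the only secondary endpoint outside safety in the visible text, and its estimate, interval, visit-wise differences and LS-mean plot all come from this model.

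At stake are the width of the interval, protection against chance imbalance, and having a single pre-specified model. Bias is not at stake, and neither is the primary endpoint.

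**Working it through.** **Plan's own figures.** The documents give no SwCl sample size, SD or correlation. The only power statement (SAP 7.2) concerns LCI2.5: 49 per arm, SD 1.5, difference -1.0. It reproduces (t-test power 90.4%; 98/0.9 = 108.9 against about 108 planned) but has no bearing on the SwCl model.

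**Inputs**
- From the documents: average of four visits (SAP 9.3.2.2); 108 subjects randomised 1:1, so 54 per arm (SAP 7.1); the effect cited from subjects aged 12 and older, "SwCl (LS mean treatment difference of -41.8 mmol/L" (Protocol 9.3.3).
- Assumed: SwCl SD 12 mmol/L; correlation ρ of 0.3 to 0.9 between any two SwCl measurements; ratio k of follow-up SD to baseline SD; baseline LCI2.5 unrelated to SwCl; complete data; the same covariance in both arms.

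**Formulas** (variance per subject, baseline variance set to 1)
- Variance of the four-visit mean: v = k²(1+3ρ)/4
- Change, baseline SwCl not in the model: U = v + 1 − 2kρ
- Change, baseline SwCl in the model: A = v − k²ρ²
- Difference: U − A = (1 − kρ)², which is never negative
- With k = 1: U = 5(1−ρ)/4, A = (1−ρ)(1+4ρ)/4, U/A = 5/(1+4ρ)
- 95% CI half-width: t(0.975, 104) × 12 × √(2 × variance/54), with t = 1.983
- One-SE chance imbalance at baseline: 12 × √(2/54) = 2.3 mmol/L, of which the unadjusted change keeps the share 1 − kρ

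**Results, k = 1**

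| ρ | U | A | U/A | SE larger by | Half-width without / with (mmol/L) | Imbalance kept (mmol/L) |
|---|---|---|---|---|---|---|
| 0.3 | 0.875 | 0.385 | 2.27 | 51% | 4.3 / 2.8 | 1.6 |
| 0.5 | 0.625 | 0.375 | 1.67 | 29% | 3.6 / 2.8 | 1.2 |
| 0.7 | 0.375 | 0.285 | 1.32 | 15% | 2.8 / 2.4 | 0.7 |
| 0.9 | 0.125 | 0.115 | 1.09 | 4% | 1.62 / 1.55 | 0.2 |

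For ρ = 0.3 without baseline SwCl, SE = 12 × √(2 × 0.875/54) = 2.16 and 2.16 × 1.983 = 4.3. With 49 per arm, both half-widths grow by √(54/49) = 1.05 and their ratio is unchanged.

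**Unequal SDs.** At k = 1.25 the SE without baseline SwCl is 28%, 11%, 2% or 4% larger at the same four values of ρ. The gain vanishes as kρ approaches 1: 0.2% at k = 1.5, ρ = 0.7, and 0% at k = 2.0, ρ = 0.5.

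**Separate correlations.** Let r be the baseline-to-follow-up correlation and w the between-visit correlation, with k = 1, so that v = (1+3w)/4, U = 1 + v − 2r and A = v − r². For r from 0.3 to 0.7 and w from 0.5 to 0.9, adding baseline SwCl makes the SE about 9% to 28% smaller. In the other direction, the SE without it is larger by 10% (r = 0.7, w = 0.9: √(0.525/0.435) = 1.10) to 38% (r = 0.3, w = 0.5: √(1.025/0.535) = 1.38).

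**Simulation checks**
- Four-visit mean change, 54 per arm, 4,000 trials per ρ, k = 1: SE ratios (without/with) of 1.51, 1.28, 1.15 and 1.04, and mean bias below 0.003 SD under both models.
- Five-visit model with unstructured covariance, 49 per arm, 1,500 runs per setting, w = 0.7, correlation 0.1 between baseline LCI2.5 and SwCl: SE ratios (with/without) of 0.76, 0.81 and 0.88 at r = 0.3, 0.5 and 0.7. Replacing baseline LCI2.5 by baseline SwCl, instead of adding it, gives the same ratios within 0.005.

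**Cost.** One degree of freedom adds about 0.5% to the SE at 98 to 108 subjects.

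**The case against.** The strongest reply is that this is loose drafting. In the primary model the continuous covariate is the baseline of the endpoint being analysed, so the same model applied to SwCl would naturally carry baseline SwCl. The protocol's wording allows that. If it is what the sponsor means, nothing is lost in precision and only the text needs correcting. This reading is plausible, perhaps likely. But the protocol hands the detail to the SAP, and the SAP names baseline LCI2.5 and makes no substitution.

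Second, no decision turns on it. Even in the least favourable case above (SE 2.16), an effect of 41.8 mmol/L is 41.8/2.16 = about 19 standard errors from zero, and the largest imbalance kept, 1.6 mmol/L, is about 4% of 41.8. This stands and limits the weight of the point.

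Third, the sizes rest wholly on assumptions. The 51% arises when follow-up visits correlate at only 0.3; with between-visit correlations of 0.5 or more the largest figure is 38%. The two arms may also differ in covariance under so large a drug effect. For example, take placebo with k = 1, ρ = 0.7 and active with k = 1.5, ρ = 0.5. The mean slope is 0.725, the mean variance falls from 0.641 to 0.565, and the SE is about 6% larger without adjustment. This too stands: the gain runs from negligible to substantial. No case shows a loss beyond the one degree of freedom.

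**Conclusion.** The point holds. As written, the SAP's SwCl model omits baseline SwCl, and following it gives an unbiased but less precise estimate. Under the equal-variance assumptions the standard error is 4% to 51% larger, or 10% to 38% larger when the between-visit correlation is set separately at 0.5 to 0.9. The excess is close to zero if the slope of follow-up on baseline is near 1. The documents supply none of the SDs or correlations, so these figures are a range and not an estimate for this trial. With a nominal P value, and if the effect is near the one cited from older subjects, the conclusion would be the same under either model. The change is worth making because it costs almost nothing and leaves one unambiguous model.

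**What to change.** In SAP 9.3.2.2, state that the SwCl MMRM includes continuous baseline SwCl as a covariate, in addition to treatment group, visit, treatment-by-visit interaction, continuous baseline LCI2.5 and the screening weight stratum. Keeping baseline LCI2.5 is reasonable because screening LCI2.5 is a stratification factor (SAP 7.3); precision alone does not decide between adding and replacing.

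The cost is one sentence, one model term and one degree of freedom. No subject is lost, since a change from baseline already requires a baseline value. SAP section 4 allows an amendment before database lock and unblinding.
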